3.4. Duration of Treatment

[figure not shown]
Subjects will be treated for at least 144 weeks during the blinded treatment phase. After Week 144, all subjects will continue to take their blinded study drug and attend visits every 12 weeks until the End of Blinded Treatment Visit. Once the last subject completes the Week 144 visit and Gilead completes the Week 144 analysis, all subjects will return to the clinic (preferably within 30 days) for an End of Blinded Treatment Visit. At the End of Blinded Treatment Visit, subjects will be given GS-9883/F/TAF FDC in an open label (OL) extension phase for 96 weeks (Week 96 OL). After Week 96 OL, subjects will discontinue the study drug, transition onto commercially available treatment and complete a 30-Day Follow-up Visit. In a country where GS-9883/F/TAF is not available, subjects will be given the option to continue OL GS-9883/F/TAF until the product becomes accessible to subjects through an access program, or until Gilead Sciences elects to discontinue the study in that country, whichever occurs first.

All subjects participating in the open label extension phase, without regard to their blinded treatment regimen, will return for study visits at Week 12 OL and every 12 weeks thereafter for 96 weeks.

Subjects who complete the study through the End of Blinded Treatment Visit and do not continue on the open label GS-9883/F/TAF FDC extension phase will be required to return to the clinic after the End of Blinded Treatment Visit for a 30-Day Follow-up visit.

Treatment assignments will be provided to the investigators within 30 days of the last subject completing the End of Blinded Treatment Visit.

Figure 3-1. Study Schema

- a Following the Day 1 visit, subjects will be required to return for study visits at Weeks 4, 8, 12, and then every 12 weeks through Week 144.
- b After Week 144, all subjects will continue to take their blinded study drug and attend visits every 12 weeks until the End of Blinded Treatment Visit.

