6.5.3. Treatment Assessments (Open-Label Rollover Extension)

For purposes of study visit identification during the open-label rollover extension, study visits will be identified by the number of weeks that have elapsed between the End of Blinded Treatment Visit and the corresponding open-label study visit, and labeled with “OL” eg. Week 12 OL, Week 24 OL, etc.

All subjects participating in the open label extension phase, without regard to their blinded treatment regimen, will return for study visits at Week 12 OL and every 12 weeks thereafter for 96 weeks.

Study visits are to be completed of the protocol-specified visit date based on the End of Blinded Treatment Visit through Week 12 OL and completed \pm 6 days of the protocol-specified visit date every 12 weeks thereafter, unless otherwise specified.

The following will be performed at the Open-Label Extension Visits:

- Review of AEs and changes in concomitant medications
- Complete physical examination (**Week 48 OL, Week 96 OL**) (urogenital/anorectal exams will be performed at the discretion of the Investigator) or symptom-directed physical examination as needed
- Vital signs measurement (blood pressure, pulse, respiration rate, and temperature), including weight
- 12-lead ECG performed supine (**Week 48 OL, Week 96 OL**)
- Urine collection for the following laboratory procedures:
 - Urinalysis
 - Urine pregnancy test (females of childbearing potential only); positive urine pregnancy tests will be confirmed with a serum test. If the test is positive, the subject will be discontinued.

CCU

- Blood sample collection for the following laboratory analyses:
 - Chemistry profile: alkaline phosphatase, AST, ALT, GGT, total bilirubin, direct and indirect bilirubin, total protein, albumin, LDH, CPK, bicarbonate, BUN, calcium, chloride, creatinine, glucose, phosphorus, magnesium, potassium, sodium, uric acid, and amylase (reflex lipase testing is performed in subjects with total amylase $> 1.5 \times$ ULN). At Weeks 24, 48, 72, and 96 OL, analyses of glucose will be done as part of the fasting metabolic assessments and not as part of the chemistry profile. In addition, TSH will also be analyzed at Week 24, 48, 72 and 96 OL.

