Subjects will be treated for at least 144 weeks during the blinded treatment phase. After Week 144, all subjects will continue to take their blinded study drug and attend visits every 12 weeks until the End of Blinded Treatment Visit. Once the last subject completes the Week 144 visit and Gilead Sciences Inc. (Gilead) completes the Week 144 analysis, all subjects will return to the clinic (preferably within 30 days) for an End of Blinded Treatment Visit. At the End of Blinded Treatment Visit, subjects will be given the option to receive B/F/TAF FDC in an open-label (OL) extension phase for 96 weeks. After Week 96 OL, subjects will discontinue the study drug, transition onto commercially available treatment and complete a 30-Day Follow-up Visit. In a country where B/F/TAF is not available, subjects will be given the option to continue OL B/F/TAF until the product becomes accessible to subjects through an access program, or until Gilead elects to discontinue the study in that country, whichever occurs first.

All subjects participating in the OL extension phase, without regard to their blinded treatment regimen, will return for study visits at Week 12 OL and every 12 weeks thereafter for 96 weeks.

Subjects who complete the study through the End of Blinded Treatment Visit and do not continue on the OL B/F/TAF FDC extension phase will be required to return to the clinic after the End of Blinded Treatment Visit for a 30-Day Follow-Up Visit.

Treatment assignments will be provided to the investigators within 30 days of the last subject completing the End of Blinded Treatment Visit.

Schedule of Assessments

After screening procedures, eligible subjects will be randomized 1:1 to Treatment Group 1 or Treatment Group 2 and treated for 144 weeks. Following the Day 1 visit, subjects will be required to return for study visits at Weeks 4, 8, and 12, and then every 12 weeks from Week 12 through Week 144. After Week 144, all subjects will continue to take their blinded study drugs and attend study visits every 12 weeks until the End of Blinded Treatment Visit. All subjects participating in the OL extension phase, without regard to their blinded treatment regimen, will return for study visits at Week 12 OL and every 12 weeks thereafter for at least 96 weeks.

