3.8.2. Analysis Windows

Subject visits might not occur on protocol-specified days. Therefore, for the purpose of analysis, observations will be assigned to two different sets of analysis windows based on the following tables: the analysis windows for the randomized phase analysis are derived relative the Study Day 1 for the randomized phase analysis, while the analysis windows for the all B/F/TAF analysis are derived relative the Study Day 1 for the all B/F/TAF analysis.

The analysis windows for HIV-1 RNA, CD4+ cell count, CD4 %, hematology, chemistry, urinalysis, urine pregnancy laboratory tests, eGFR_{CG}, vital signs, and weight (if collected) are presented in [Table 3-1](#) and [Table 3-2](#) for the randomized phase analysis and the All B/F/TAF analysis separately.

Table 3-1. Analysis Windows for HIV-1 RNA, CD4+ cell count, CD4 %, HBV DNA, Hematology, Chemistry, Urinalysis, Urine Pregnancy Laboratory Tests, eGFR_{CG}, Vital Signs, and Weight for the Randomized Phase Analysis

Visit ID	Nominal Day	Lower Limit	Upper Limit
Baseline			1
Week 4	28	2	42
Week 8	56	43	70
Week 12	84	71	126
Week 24	168	127	210
Week 36	252	211	294
Week 48	336	295	378
Week 60	420	379	462
Week 72	504	463	546
Week 84	588	547	630
Week 96	672	631	714
Week 108	756	715	798
Week 120	840	799	882
Week 132	924	883	966
Week 144	1008	967	1050
Week K (K is every 12 weeks after previous visit)	K*7	(K-6)*7+1	(K+6)*7

Table 3-2. Analysis Windows for HIV-1 RNA, CD4+ cell count, CD4 %, HBV DNA, Hematology, Chemistry, Urinalysis, and Urine Pregnancy Laboratory Tests, eGFR_{CG}, Vital Signs, and Weight for the All B/F/TAF Analysis

Visit ID	B/F/TAF Group			DTG/F/TAF to B/F/TAF		
	Nominal Day	Lower Limit	Upper Limit	Nominal Day	Lower Limit	Upper Limit
Baseline			1			1
Week 4	28	2	42	NA	NA	NA
Week 8	56	43	70	NA	NA	NA
Week 12	84	71	126	84	2	126
Week 24	168	127	210	168	127	210
Week 36	252	211	294	252	211	294
Week 48	336	295	378	336	295	378
Week 60	420	379	462	420	379	462
Week 72	504	463	546	504	463	546
Week 84	588	547	630	588	547	630
Week 96	672	631	714	672	631	714
Week k	K*7	(K-6)*7+1	(K+6)*7	K*7	(K-6)*7+1	(K+6)*7

NA = Not applicable

Note: For the B/F/TAF group, Study Day 1 is the first dose date of the B/F/TAF received in the randomized phase;

Note: For the DTG/F/TAF to B/F/TAF group, Study Day 1 is the first dose date of the B/F/TAF received in the extension phase.

Note: Week k is every 12 weeks after previous visit.

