Week 48	336	253	504	336	2	504
Week 96	672	505	840	672	505	840
Week k	K*7	(K-24)*7+1	(K+24)*7	K*7	(K-24)*7+1	(K+24)*7

Note: For the B/F/TAF group, Study Day 1 is the first dose date of the B/F/TAF received in the randomized phase;
 Note: For the DTG/F/TAF to B/F/TAF group, Study Day 1 is the first dose date of the B/F/TAF received in the extension phase.
 Note: Week k is every 48 weeks after previous visit.
 NA=Not Applicable.

3.8.3. Selection of Data in the Event of Multiple Records in an Analysis Window

Depending on the statistical analysis method, single values are required for each analysis window. For example, change from baseline by visit usually requires a single value, whereas a time to event analysis would not require one value per analysis window. When a single value is needed, the following rule(s) will be used.

If multiple nonmissing numeric observations exist in a window, then records will be chosen as follows:

- For baseline, the latest available record on or prior to the first dose date of study drug will be selected. If there are multiple records with the same time or no time recorded on the same day, average will be used for the baseline value, except for HIV-1 RNA (see below).
- For postbaseline visits:
 - For CD4+ cell count, CD4%, and HBV DNA, the record(s) collected on the latest day in the window will be selected for analysis.
 - For other numeric observations (ie, except HIV-1 RNA, CD4+ cell count, CD4%, and HBV DNA), the record(s) collected on the day closest to the nominal day for that visit will be selected. If there are 2 days equidistant from the nominal day, the later day will be selected.
 - For any numeric observations except HIV-1 RNA, if there are multiple records on the selected day, the average will be taken.
- For baseline and postbaseline HIV-1 RNA, the latest (considering both date and time) record(s) in the window will be selected. If both “HIV RNA Taqman 2.0” and “HIV RNA Repeat” (ie, the HIV-1 RNA result obtained from an additional aliquot of the original sample) are available with the same collection time, the results from the “HIV RNA Repeat” will be selected for analysis purposes; otherwise, if there are multiple “HIV RNA Taqman 2.0” records with the same collection time, the geometric mean will be taken for analysis purposes.

If multiple valid nonmissing categorical observations exist in a window, records will be chosen as follows:

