6.3.2. Analysis of the Efficacy Endpoints for All B/F/TAF Analysis

6.3.2.1. Analysis of the Proportion of Subjects with HIV-1 RNA < 50 copies/mL by and Missing = Excluded and Missing = Failure Approaches

The proportion of subjects with HIV-1 RNA < 50 copies/mL will be analyzed using M = E for imputing missing HIV-1 RNA values using the All B/F/TAF Analysis Set for the all B/F/TAF analysis.

- Missing = Excluded (M = E)

In this approach, all missing data will be excluded in the computation of the percentages (ie, missing data points will be excluded from both the numerator and denominator in the computation). The denominator for percentages at a visit is the number of subjects in the all B/F/TAF analysis set with nonmissing HIV-1 RNA value at that visit.

- Missing = Failure (M = F)

In this approach, all missing data will be treated as HIV-1 RNA \geq 50 copies/mL. The denominator for percentages is the number of subjects in all B/F/TAF analysis set.

For M = E and M=F analyses, the number and percentage of subjects with HIV-1 RNA in the following categories will be summarized:

- < 50 copies/mL
 - < 20 copies/mL
 - < 20 copies/mL Not Detectable
 - < 20 copies/mL Detectable
 - 20 to < 50 copies/mL

- 50 to < 200 copies/mL
- 200 to < 400 copies/mL
- 400 to < 1000 copies/mL
- ≥ 1000 copies/mL
- Missing (only applicable for M=F analysis)

For all B/F/TAF analyses, the 95% CI for the proportion of subjects with HIV-1 RNA < 50 copies/mL for a treatment group will be constructed using the Clopper-Pearson exact method.

For M =F analysis, results will be summarized by visit up to Week 240 for B/F/TAF group and up to Week 96 for DTG + F/TAF to B/F/TAF group. For the M = E analysis, results will be summarized by treatment group for all visits through the end of study. No statistical comparison will be made for the all B/F/TAF analysis.

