- k Subjects who complete the open-label rollover extension will be required to return to the clinic 30 days after the completion of study drugs for the 30-Day Follow-Up Visit. Subjects who permanently discontinue study drugs during the open-label rollover extension will be asked to return to the clinic 30 days after the completion of the Early Study Drugs Discontinuation Visit for the 30-Day Follow-Up Visit. For the purpose of scheduling a 30-Day Follow-Up Visit, a ± 6 days window may be used.
- l Study visits are to be completed within ± 2 days of the protocol-specified visit date based on the End of Blinded Treatment Visit date through Week 12 OL and completed within ± 6 days of the protocol-specified visit date every 12 weeks thereafter, unless otherwise specified
- m For subjects who meet the definition of HBV infection at any visit: The following will be conducted by the central laboratory: HBsAb, HBsAg (qualitative and quantitative) and HBeAg (if negative, reflex HBeAb) (every 24 weeks) and Plasma HBV DNA (every 12 weeks). For subjects who do NOT meet the definition of HBV infection at any visit: The following will be conducted by the central laboratory: Hepatitis B surface antibody (HBsAb), Hepatitis B virus core antibody (HBcAb), and Hepatitis B virus surface antigen serology (HBsAg). Subjects who are HBsAg and/or HBcAb positive will have a reflex test for HBV DNA (viral load) (Weeks 48 OL and 96 OL)
- n Hepatitis C virus (HCVAb) serology. Subjects who are HCVAb positive will have a HCV RNA test performed. (Weeks 48 OL and 96 OL).
- o After Week 96 OL, if subject is in a country where GS-9883/F/TAF is not available, the study procedures completed by the subject will be the same at every 48 weeks (i.e. OL Weeks 48, 96) and at every 12 weeks (i.e. OL Weeks 12, 24, 36, 60, 72, 84) until the product becomes accessible to subjects through an access program, or until Gilead Sciences elects to discontinue the study in that country, whichever occurs first.

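### Some B/F/TAF-arm subjects who attend every open-label visit can still have an empty HIV-1 RNA window, which Missing = Failure then scores as failure

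*SAP*

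**What the plan says.** **When open-label visits happen.** The End of Blinded Treatment Visit has one calendar trigger for everyone: "Once the last subject completes the Week 144 visit and Gilead Sciences Inc. (Gilead) completes the Week 144 analysis" (SAP Section 1.2). Until then subjects "attend visits every 12 weeks until the End of Blinded Treatment Visit" (Protocol Section 3.4). In the extension, "study visits will be identified by the number of weeks that have elapsed between the End of Blinded Treatment Visit" and the open-label visit (Protocol Section 6.5.3). The tolerance is ± 2 days through Week 12 OL, and visits are then "completed within ± 6 days of the protocol-specified visit date every 12 weeks thereafter" (SAP Appendix Table 2, note l; Protocol Appendix 3 agrees).

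**How results are assigned to weeks.** The notes to SAP Table 3-2 give two anchors: "For the B/F/TAF group, Study Day 1 is the first dose date of the B/F/TAF received in the randomized phase", whereas "For the DTG/F/TAF to B/F/TAF group, Study Day 1 is the first dose date of the B/F/TAF received in the extension phase". After Week 96 both groups use windows from (K−6)×7+1 to (K+6)×7, one every 12 weeks. When a window holds more than one HIV-1 RNA result, "the latest (considering both date and time) record(s) in the window will be selected" (SAP Section 3.8.3). No rule passes a surplus result to an empty neighbouring window.

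**How an empty window is scored.** Under M=F, "In this approach, all missing data will be treated as HIV-1 RNA" at or above 50 copies/mL, over the whole All B/F/TAF Analysis Set. Results are shown by visit up to Week 240 for the B/F/TAF group and up to Week 96 for the other group (SAP Section 6.3.2.1).

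**The concern.** The calendar trigger means that the restart falls at an arbitrary point on each B/F/TAF subject's own Day 1 grid. Where it falls close to a window edge, each later open-label visit is also scheduled close to an edge, and a few days early or late decides which window receives the sample. A sample that slips into the next window leaves its own empty, and M=F cannot tell that from a missed visit.

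M=F at the open-label weeks is a secondary endpoint in Protocol Section 3.1, and SAP Section 6.2.1 hands it to Section 6.3. The restart comes no earlier than about Week 144 and the extension lasts 96 weeks, so Week 240 lies within the planned follow-up of subjects who roll over. A suppressed full attender should not be a failure there. The error can only lower the B/F/TAF figure, and it does not touch the DTG/F/TAF to B/F/TAF figure.

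**Working it through.** **1. Reproduce the windows.** For K = 96: (96−6)×7+1 = 631 and (96+6)×7 = 714, as printed in Table 3-2. For K = 240: 1639 to 1722. Every window from Week 24 on is 84 days wide and abuts the next.

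**2. Visits exactly on schedule.** Spacing (84 days) equals window width (84 days), so each window receives exactly one visit whatever the restart day. No window is empty. The shifted anchor alone does no harm.

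**3. Condition for an empty window.** Let t be the distance from a scheduled visit to the nearby window edge, and let J1 and J2 be the deviations of that visit and the next from schedule. The window between them is empty only if J1 falls short of t and J2 goes past it. With deviations within ± 6 days this needs t between −6 and +6, that is 12 of 84 possible offsets, or 14% (1 in 7).

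**4. Example.** The End of Blinded Treatment Visit is on Day 1134, the last day of the Week 156 window.
- Week 36 OL is due on Day 1134 + 252 = 1386 and attended on Day 1389 (+3).
- Week 48 OL is due on Day 1470 and attended on Day 1468 (−2).
- The Week 192 window is Days 1303 to 1386 and the Week 204 window is Days 1387 to 1470.
- Both samples fall in Week 204, where only the later is used. If Week 24 OL (due Day 1302) was not attended late, Week 192 is empty and M=F scores it as failure.

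**5. Average size.** The documents give neither the restart offsets nor the visit deviations, so both are assumed: offsets evenly spread over the 84 days, deviations independent. With F the distribution of a deviation, the expected empty fraction is the integral of F(t)×(1−F(t)) over t, divided by 84.
- Uniform within ± 6 days: 12/6 = 2 days; 2/84 = 2.4%. In whole days (13 equally likely values): (13²−1)/(6×13) = 2.15 days; 2.15/84 = 2.6%.
- Normal, SD 3 days: 3/√π = 1.69 days; 1.69/84 = 2.0%.
- Uniform within ± 2 days: 4/6 = 0.67 days; 0.67/84 = 0.8%.
- Restart exactly on an edge: F×(1−F) peaks at ½×½, about 25% per window. Restart 7 or more days from an edge: 0%.

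**6. Simulation check.** 200,000 subjects with no missed visit, whole-day deviations, ± 2 days at Week 12 OL and the restart 60 to 396 days after Day 1008 (assumed). Empty windows at Weeks 216, 228 and 240 were 2.5%, 2.6% and 2.6% with uniform ± 6 days, and 1.8%, 2.0% and 1.9% with SD 3 days truncated at ± 6. Earlier weeks were lower (0.2% at Week 168 with uniform deviations) because many subjects had not yet restarted. No window through Week 156 was empty.

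**7. Effect on the reported percentage.** The shift is the empty fraction times the share of the full set who are suppressed full attenders. If, for illustration, that were 240 of 300: 2.4% × 240 = 5.8 subjects, so 240/300 = 80.0% (Clopper-Pearson 75.0% to 84.4%) would be reported as about 234/300 = 78.0% (72.9% to 82.6%).

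**8. The other group.** Its windows start from the first open-label dose. If that dose is taken at the End of Blinded Treatment Visit, a visit due 84k days later falls on Study Day 84k+1, which is 42 days from the lower window limit and 41 from the upper. A 6-day deviation cannot empty a window.

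**The case against.** The strongest reply is that the effect is small, conservative and visible. It runs against the sponsor's product. The M=F table has its own Missing row, so empty windows are not mixed with observed values at or above 50. M=E is reported for the same visits and drops them. The shift is smaller than the Clopper-Pearson half-width (about 4.7 points at 240/300). SAP Sections 3 and 6.3.2.1 rule out any comparison between the groups. The size also rests on timing distributions that the documents do not give.

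Most of this stands, and it limits the point. Two parts do not remove it. The Missing row cannot separate a sample that was never taken from one that was taken and filed in the next window. The confidence interval describes sampling error and does not correct an error that always runs one way.

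A reader might infer that full attenders in general get empty windows. They do not: visits on schedule empty no window at any offset, and about 6 in 7 restarts are not exposed at all. A reader might also infer that the contrast between the two columns is spoiled. The documents plan no such contrast, and the columns already differ by construction: under SAP Section 3.2 the B/F/TAF group keeps subjects who never rolled over, while the other group holds only those who did.

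**Conclusion.** The point holds in a limited form. The rules as written misclassify some suppressed B/F/TAF-arm subjects who missed no visit, namely those whose restart falls within about 6 days of a window edge and whose successive visits deviate unequally. Under even spread of restarts and in-tolerance timing, the M=F rate among full attenders is lowered by about 2 points per visit at Weeks 216 to 240 (range about 0.8 to 2.4; 2.6 if counted in whole days). Over the full-set denominator the loss is smaller. The actual size can be read from the visit dates.

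M=E, windows through Week 144, the primary endpoint and the Week 48, 96 and 144 snapshot endpoints are unaffected. This is a small, avoidable bias in a descriptive secondary result. It should be corrected, but it threatens no conclusion of the trial.

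**What to change.** For B/F/TAF-arm HIV-1 RNA after the End of Blinded Treatment Visit:
- Window each sample around its scheduled open-label date, 84k days after the End of Blinded Treatment Visit or the first open-label dose (state which), in 84-day windows, as Table 3-2 already does for the other group.
- Report each open-label visit under the cumulative week whose Table 3-2 window contains that scheduled date. Scheduled dates are 84 days apart, so each later week receives exactly one visit.
- Leave Table 3-2 unchanged for blinded-phase samples and for subjects who do not roll over.

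In the example above, the Day 1389 sample is reported at Week 192 and the Day 1468 sample at Week 204. Each sample is assigned to one window only, full attenders have no empty window, and genuine misses and discontinuations still count as failures.

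The cost is one extra windowing rule and its programming. A sample's actual day may lie up to about 6 days outside the Day 1 window under which it is reported, which a footnote can state. SAP Section 1 already provides for documenting later changes in the study report.

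Filling an empty window from the nearest neighbouring result would be a weaker repair. In simulation about 70 to 80% of such fills reuse a result already scored in its own window, and the rule can also fill a window after a genuine miss or after the drug was stopped.
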